3.1.1.1 Part 1: Single-Ascending Dose (SAD) in Healthy Volunteers

Part 1 is a randomized, Sponsor-open, Investigator-blinded, subject-blinded placebo-controlled, adaptive SAD study with an adaptive dose-escalation schedule. The first cohort will receive a single dose of 0.1 mg/kg RO7062931 or placebo using a 4:1 randomization scheme. [REDACTED]

[REDACTED]

However, at this dose, AEs are expected to be mild and within this protocol higher doses may be evaluated if this dose is found to be safe and well tolerated. [REDACTED]

[REDACTED]

The use of a Bayesian analysis, specifically a continual reassessment method (CRM) analysis will be explored as a tool to help to guide the selection of these additional doses and is explained in further detail in the exploratory analysis (Section 6.8). There will be ongoing assessment of available safety, tolerability, and PK data prior to initiation of the next dose and cohort.

[figure not shown]
Eight HVs receiving RO7062931 and two receiving placebo are planned to be enrolled in each cohort of Part 1. The HVs will be admitted to the clinic on Day – 1 and discharged on Day 3, following the morning assessments. Ambulatory visits will be performed as indicated in the SoA tables (see [Appendix 1](#) to [Appendix 2](#)). The HVs of each cohort will receive sentinel dosing, where two subjects will be dosed on Day 1, at least one of which will receive RO7062931 to monitor acute reactions and the remaining 8 subjects can be dosed on the following day (24 hours afterwards) following satisfactory safety assessments of the first two subjects by the Investigator. Following the single dose of all HVs in a cohort, safety will be monitored for at least 28 days prior to escalation to the next dose cohort.

3.1.1.2 Part 2a/2b: Proof-of-Mechanism in CHB Infected Patients

Part 2a/b is a multi-center randomized, Sponsor-open, Investigator-blinded, subject-blinded, placebo-controlled, adaptive, parallel multiple-dose study in chronically HBV infected patients, with the aim to study the safety, tolerability, PK of RO7062931 (and if applicable metabolite[s]), and the relationship between RO7062931 dose, dose regimen and viral dynamic response.

In Part 2a, CHB patients will receive two monthly doses (Q1M) of RO7062931. Part 2a is planned to consist of 4 parallel cohorts of 3 RO7062931 dose levels and one placebo.

In addition to safety, PK will be evaluated in the first two patients of each dose cohort prior to subsequent randomization to confirm that RO7062931 exposure is comparable as found for the HVs. Cohort doses may be adjusted across the patient cohorts if plasma PK appears to significantly differ from the HVs. Each cohort in Part 2a will consist of 6 patients.

In Part 2b, a dose identified from the dose-response analysis of Part 2a (based on either HBsAg decline or maximum dose evaluated and well tolerated) will be tested in different dosing regimens administered weekly (QW) or bi-weekly (Q2W). The total dose of 400 mg per day will not be exceeded. The selection of dosing regimens will be guided by the analysis of safety, PK and PD data of all previous cohorts in Part 2.

In Part 2b, each patient will be randomized to active or placebo in each dose cohort/level in a 3:1 ratio. Each cohort in Part 2b will be comprised of 8 patients, six patients will receive RO7062931 and two will receive placebo. CHB patients will be followed up weekly for the first 28 days and then monthly up to at least 84 days after the last dose of RO7062931.

There will be two optional overnight stay periods for the patients: between Day –1 and Day 2, and between Day 29 and Day 30 (exception: between Day 22 and Day 23 for the cohort with 4 doses given QW). If the Investigator agrees, the patients can leave the clinic after completing the last evening assessment and return the following morning prior to the first scheduled assessment. In Part 2b, where drug administration is given on days other than Day 1 and Day 29 (or Day 22 for the cohort with 4 doses given QW), the patients will be administered the drug in the clinic as an ambulatory visit.

Visits and assessments will be performed as indicated in the SoA tables (see [Appendix 3](#) to [Appendix 14](#)).

All doses in Part 2 will be lower than, or equal to, the doses studied and considered to be well-tolerated in Part 1. Subsequent doses and regimens for Part 2b/2c will be selected on the basis of the analysis of Part 2a data. Part 2b will be initiated once Part 2a data have been analyzed. *The* total dose will not exceed 400 mg per day.

Due to the adaptive nature of this study, the actual number of dose levels and the number of study subjects/cohorts at each dose may be modified depending on emerging data. Planned doses may be adjusted (increased, decreased, or repeated) or dosing may be discontinued. After safety and PK data review (see Section [3.1.4](#)), study subjects may be requested to return to the site for additional safety or PK assessments, upon agreement between subjects, Investigators and the Sponsor.

3.1.1.3 *Part 2c: Extended Duration of RO7062931 Therapy in CHB Infected Patients*

Part 2c is an adaptive, open-label, non-controlled, multi-arm, multi-center, study to evaluate the efficacy and safety of RO7062931 following subcutaneous administration on top of SoC therapies (a NUC with/without PEG-IFN) in NUC-suppressed or treatment-naïve CHB patients ([Figure 2](#)). Both HBeAg positive and negative patients will be enrolled.

- *Cohort 9 will enroll NUC-suppressed CHB patients. Patients will receive RO7062931 on top of a NUC for up to 24 weeks. RO7062931 will be administered at a dose determined from study Parts 2a and 2b.*
- *Cohort 10 will enroll NUC-suppressed CHB patients. Patients will receive RO7062931 on top of a NUC plus PEG-IFN for up to 48 weeks. RO7062931 will be administered at a dose determined from study Parts 2a and 2b.*
- *Cohort 11 and 12 (optional cohorts) may enroll treatment-naïve immune-active CHB patients and/or different treatment combinations or treatment duration.*

All cohorts will initially enroll approximately 8 CHB patients per cohort. Initially the enrollment will occur sequentially (Cohort 9 will be followed by Cohort 10, see Section 4.3). At the end of treatment (either 24 or 48 weeks depending on cohort), all study treatment (RO7062931 and PEG-IFN) will be discontinued and all patients will be followed up for at least 24 weeks post-treatment follow up.

Based on emerging and accumulated PK, PD, efficacy and safety data from this study or other related studies, the initial cohorts may be expanded to enroll a total of 30 CHB patients. Enrollment of the expanded cohorts may be either sequential or parallel.

3.1.2 Dose-Review/Escalation Decisions

Dose-escalation/review meetings will be conducted by the Investigator, the Medical Monitor, and the Sponsor Clinical Team prior to each RO7062931 dose-escalation (see Section 3.1.4). The study will have an adaptive dosing design and the actual doses may be modified based on emerging safety, tolerability, PK and PD data, but with dose-escalation ratios not higher than currently projected (i.e., with more conservative escalations at higher dose levels). The decision to escalate to the next dose level, or add an additional cohort at a previously studied dose, will be made following the review of the following data from the completed cohort:

For Part 1

- All available safety information, including AEs, ECGs, vital signs, clinical laboratory test results collected up to Day 29 visit.
- All available PK data collected over ≥ 1 week post-dose to characterize the RO7062931, and if available, its metabolite(s) and predict exposure in the following cohort(s).

For Parts 2a/2b

- All available safety information, including AEs, ECGs, vital signs, clinical laboratory test results collected up to Day 57 visit (exception: Day 50 for the cohort with 4 doses given QW).
- Adequate data over the first week in Part 2a to characterize the RO7062931 PK and predict exposure in cohorts with different regimens or doses used in Part 2b.
- HBsAg levels at least by two weeks after the last dose.

For Part 2c

- *Commencement of optional cohorts, or expansion of existing cohorts, will be determined based on accumulated safety, tolerability, PK, and PD data from this study.*

3.1.2.1 Part 1 Dose- Escalation Decision Criteria

Part 1 uses an adaptive dose-escalation schedule that may be modified if:

- [REDACTED]
- Events emerge that the Sponsor and/or Investigator consider indicators that the planned dose-escalation step would result in unacceptable risks for the safety of the HVs.
- The Sponsor and Investigator agree to do so and neither considers that the proposed subsequent dose level poses an unacceptable risk to the study subjects.

Single doses will not be escalated if the dose-escalation stopping criteria are met (see Section 3.1.3.1) but may exceed the proposed maximum dose level of 4 mg/kg only if anticipated to be safe and necessary to generate additional PK or PD data in support of dosing regimens for use in Part 2 of the study.

3.1.3 Dose-Escalation Stopping Criteria

3.1.3.1 Part 1

Dose-escalation in Part 1 will not be implemented as planned in healthy volunteers dosed with RO7062931, and dosing for a treatment arm/cohort in Part 2 will be discontinued, if one of the below criteria is fulfilled, unless it is obvious that the occurrence is not considered to be related to RO7062931.

Dose-escalation will be stopped if at a dose level, more than 2 of 8 healthy volunteers receiving RO7062931 in Part 1 or, within a treatment arm/cohort in Part 2, more than 2 of 6 patients experience:

- Severe or clinically significant (as defined by the Investigator) RO7062931-related AEs of the same character, or
- Significant RO7062931-related laboratory abnormality of the same character, or
- Clinically significant RO7062931-related changes in vital signs or ECGs of the same character (e.g., QTcF > 500 msec, or > 60 msec longer than the pre-dose baseline, within the first 48 hours post-dose).
- Within two consecutive dose cohorts, four occurrences of any of the above conditions in HVs receiving active drug.

Other findings (regardless of the incidence rates) that at the joint discretion of the Sponsor and the Investigator indicate that dose-escalation (in Part 1) or dosing (in Part 2) should be halted (see Section 4.7).

3.1.3.2 Part 2

In Part 2, in case a cohort is stopped, alternative regimens within a previously tolerated dose/monthly-exposure range could be further investigated or a regimen repeated in the subsequent cohorts by mutual agreement between the Sponsor and Investigator, in order to increase the amount of data within the tolerated dose/monthly-exposure range. Due to the exploratory nature of this clinical study, its conduct can be discontinued at any time at the discretion of the Sponsor.

3.1.4 Communication Strategy

After each subject receives RO7062931 (or placebo), the Investigator(s) must confirm to the Sponsor that the subject (HV or patient) has been dosed and provide a brief summary of the status of the subject in terms of safety and tolerability to RO7062931/placebo (this will be communicated by email and/or telephone). In Part 1 of the study, the Investigator(s) will provide a safety assessment feedback of the first two sentinel dosing HVs of each cohort.

In case of a safety concern, the Investigator will contact the Sponsor immediately to discuss study subject status and action taken/to be taken. In addition, after each cohort in Part 1 has been completed and after completion of Part 2a and Part 2b, the Sponsor will organize a teleconference with the investigators to discuss the safety and tolerability of RO7062931 and to discuss eventual next cohort(s) or continuation (Part 2a and Part 2b). The next recommended dose-level (supported by nCRM, if appropriate, for Parts 1 and 2b) will be discussed by Sponsor and investigators. During these teleconferences, adverse events (with severity assessed as given in Section 5.3.3, [Table 2](#)) in addition to available safety laboratory results, vital signs, ECGs, will be discussed along with the results of the available PK data, and any other available data that may assist the dose-escalation decision process. The decision of these meetings will be documented in writing.

In addition to these communications, the Sponsor and investigators will be in regular contact throughout the study by email/telephone as per normal interactions during the conduct of a clinical study and the Sponsor will arrange regular teleconferences and meetings to discuss study status.

3.1.5 End of Study

The end of the study is defined as the last patient last visit (LPLV) per protocol (includes the safety and follow-up visit) or the date at which the last data point from the last patient required for statistical analysis is received, whichever is the later date, unless the patient was prematurely discontinued.

3.2 RATIONALE FOR STUDY DESIGN

A two-part study design has been chosen to characterize RO7062931 in this clinical trial. In Part 1, safety and PK of single RO7062931 doses will be characterized in healthy volunteers to determine the best liver-targeted dose to be evaluated in CHB patients. In Part 2, safety, PK, HBsAg decline and other possible PD effects will be assessed following multiple RO7062931 doses in CHB patients and data will be obtained to further refine the dose and dosing regimen. *Part 2c will evaluate the efficacy and safety of RO7062931 when administered with SoC for up to 48 weeks.*

3.2.1 Rationale for Dosage Selection

A starting dose of 0.1 mg RO7062931 per kg has been selected for this first study in humans. [REDACTED]

[REDACTED] Therefore, the starting-dose of 0.1 mg/kg represents the lower end of the predicted therapeutic dose range in humans and would be expected to have little or no measureable pharmacodynamic effect if evaluated in CHB patients.

A two-pronged approach to the calculation of safety multiples was taken, in that calculations were based, respectively, on plasma and liver levels. By applying the PK model for scaling to human PK, the expected AUC_{0-24h} in plasma, and liver concentration at 168 hours post-dose, were derived and compared to the corresponding values obtained at the NOAEL in the GLP toxicity studies. [REDACTED]

For the calculations of safety margins, the anticipated efficacious dose level was conservatively [REDACTED], which is the upper part of the predicted range. While liver exposure is more relevant to the nature of the prevailing preclinical target organ (the liver), plasma exposure is expected to be more relevant to the other potential AEs (e.g., renal). [REDACTED]

3.2.2 Rationale for Study Population

Part 1 will be conducted in healthy male and female subjects of non-childbearing potential, 18 to 65 years of age. The absence of confounding diseases and co-medications in healthy volunteers allows for a more consistent and comprehensive assessment of drug disposition and safety profile to be obtained.

Part 2a/2b will be conducted in nucleoside/nucleotide suppressed CHB infected patients. Only in this patient population can the pharmacodynamic effects of RO7062931 in humans be tested. The PK and safety of RO7062931 will also be evaluated in this population. The results will provide essential information for supporting the future development, such as dose-selection for a Phase II study in CHB patients.

Part 2c of the study will be conducted in NUC-suppressed or potentially treatment-naïve immune-active CHB patients, and will include both HBeAg positive and HBeAg negative patients. These patient populations are considered appropriate for trials of novel CHB therapeutics regimen, as highlighted in current guidelines (FDA 2018).

3.2.3 Rationale for Control Group

[figure not shown]
This phase I study is designed to be adequate and well-controlled. In Part 1, randomization to RO7062931 or placebo will occur in a 4:1 ratio within each of the up to 8 cohorts planned. This is considered sufficient to allow for comparisons of safety and tolerability of active to placebo both within and across cohorts.

In Part 2a, randomization to 3 doses of active or placebo will occur in a 1:1:1:1 ratio. In Part 2b, randomization to active or placebo will be 3:1 (within cohorts). The assessment of dynamic changes of HBsAg in CHB patients, will allow estimating the effect of RO7062931 over placebo. The control patients will also allow for the comparisons of safety of active with placebo.

[figure not shown]
[figure not shown]
It is not considered necessary to include controls within the cohorts of Part 2c. Part 2a and 2b have shown that placebo controls have negligible change in HBsAg levels over time. This information can be leveraged in Part 2c for interpretation of HBsAg dynamics. The safety data from Part 2c will be compared qualitatively against Part 2a and Part 2b placebo data and against well-established historical safety profiles of SoC therapies.

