NUCs (entecavir, tenofovir alafenamide or tenofovir disoproxil fumarate) to be used as background SoC therapies in Part 2c are classed as non-investigational medicinal product.

PROCEDURES

A Schedule of Assessments (SoA) is provided.

ROCHE RESEARCH BIOSAMPLE REPOSITORY (RBR)

The Roche Research Biosample Repository (RBR) is a centrally administered group of facilities for the long-term storage of human biological specimens, including body fluids, solid tissues and derivatives thereof (e.g., DNA, RNA, proteins, peptides). The collection, storage and analysis of these specimens will facilitate the rational design of new pharmaceutical agents and the development of diagnostic tests, which may allow for individualized drug therapy for patients in the future.

Unused residual PD serum, plasma and blood samples will be retained as well as specimens will be collected from patients who give specific consent to participate in this optional Research Biosample Repository. Collected specimens will be used to study the association of biomarkers with efficacy, adverse events, or disease progression, to study drug response, including drug effects and the processes of drug absorption and disposition, and to increase the knowledge and understanding of the disease biology. These samples will also aid in the development of biomarker or diagnostic assays and establish the performance characteristics of these assays. The following samples will be collected for identification of dynamic (non-inherited) biomarkers:

- Leftover serum and plasma samples to assess protein biomarkers including, but not limited to proteomics.

The following samples will be collected for identification of genetic (inherited) biomarkers:

- Blood for DNA extraction to assess for biomarkers, including but not limited to the following: single nucleotide polymorphisms (SNPs)

The samples collected for DNA extraction may be used for whole genome sequencing (WGS) and other genetic analysis and may be sent to one or more laboratories for analysis.

STATISTICAL METHODS

All study subjects randomized to receive placebo will be pooled as control group for Part 1. Patients receiving placebo in Part 2b will be pooled with the placebo cohort from Part 2a.

PHARMACODYNAMIC ANALYSES

Viral Dynamic Response Analyses

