3. STUDY DESIGN

3.1 DESCRIPTION OF STUDY

3.1.1 Overview of Study Design

The study will be conducted in two parts, of which Part 1 will be in healthy volunteers and Part 2 will be in CHB patients (see Figure 1). Both parts of the study are randomized. Part 1 will evaluate the safety, tolerability and PK of RO7062931, and if applicable metabolite(s), following SC administration of single doses in healthy volunteers. Part 2 will evaluate the safety, tolerability PK and PD (viral dynamics) following administration of multiple SC doses of RO7062931 in CHB patients *over a short treatment duration* (Figure 1) and *extended treatment durations* (Figure 2) (see Section 4.6).

Figure 1 Study Design: Parts 1, 2a, and 2b Short Treatment Durations

[figure not shown]
[figure not shown]

Figure 2 Study Design: Part 2c - Extended Treatment Durations

The total duration of the study for each HV in Part 1 will be ≥ 16 weeks.

- Part 1 (1 dose)
 - Screening: Up to 28 days;
 - In Clinic period: Days – 1 to 3;
 - Safety Follow-up: up to at least Day 85.

The total duration of the study for each patient in Part 2 will be ≥ 24 weeks, *except for Part 2c where the total duration may be ≥ 52 weeks.*

- Part 2a (2 doses, Q1M)
 - Screening: Up to 56 days;
 - In Clinic period (optional): Days – 1 to 2 and Days 29 to 30;
 - Safety Follow-up: up to at least Day 113.
- Part 2b (3 doses, Q2W)
 - Screening: Up to 56 days;
 - In Clinic period (optional): Days – 1 to 2 and Days 29 to 30;
 - Safety Follow-up: Up to at least Day 113.
- Part 2b (4 doses, QW)
 - Screening: Up to 56 days;
 - In Clinic period (optional): Days –1 to 2 and Days 22 to 23;
 - Safety Follow-up: Up to at least Day 106.

- Part 2b (5 doses, QW)
 - Screening: Up to 56 days;
 - In Clinic period (optional): Days – 1 to 2 and Days 29 to 30;
 - Safety Follow-up: Up to at least Day 113.
- Part 2c (QW)
 - Screening: Up to 28 days;
 - Treatment period: Up to 48 weeks;
 - Follow-up period: Up to 24 weeks.

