5.3.1 Adverse Event Reporting Period

Investigators will seek information on adverse events at each study subject contact. All adverse events, whether reported by the study subject or noted by study personnel, will be recorded in the study subject's medical record. Adverse events will then be reported on the Adverse Event eCRF as follows:

After informed consent has been obtained **but prior to initiation of study drug**, only serious adverse events caused by a protocol-mandated intervention should be reported (e.g., serious adverse events related to invasive procedures such as biopsies). Any other adverse event should not be reported.

After initiation of study drug, all adverse events, regardless of relationship to study drug, will be reported until the last follow-up visit.

After the last follow-up visit, investigators should report any deaths, serious adverse events, or other adverse events of concern that are believed to be related to prior treatment with study drug (see Section 5.6).

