6. STATISTICAL CONSIDERATIONS AND ANALYSIS PLAN

Statistical summaries will be descriptive in nature and will be reported separately for each part of the study within the clinical study report. All study subjects who are randomized to receive placebo in Part 1 will be pooled as a respective placebo control group for Part 1. Placebo from Part 2b will be pooled with the placebo cohort from Part 2a.

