6.5 SAFETY ANALYSES

All safety analyses will be based on the safety analysis population.

All study subjects who receive at least one dose of study drug will be included in the safety analysis. The safety data, including AEs, ISRs, reason for withdrawal from study, laboratory data, ECG, concomitant medications, vital signs and physical examination results will be listed and summarized descriptively. Marked abnormalities will be flagged for laboratory data.

As appropriate, listings, summary tables and graphs (study subject plot and/or mean plots) will be provided for safety and tolerability assessments.

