6.5.1 Adverse Events

The original terms recorded on the eCRF by the Investigator for adverse events will be standardized by the Sponsor by assigning preferred terms. Adverse events will be summarized by mapped term and appropriate thesaurus level.

AEs will be described by individual listings and frequency tables broken down by body system.

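### Part 2c safety is to be set beside Part 2a/2b placebo, but adverse-event and laboratory-abnormality incidence accumulate over about 48 or 72 weeks in one and 15 to 16 weeks in the other, with no common window planned

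*Combined protocol and SAP*

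**What the plan says.** Section 3.2.3 gives Part 2c no concurrent control and says its safety data will be "compared qualitatively against Part 2a and Part 2b placebo data and against well-established historical safety profiles of SoC therapies". The placebo group is formed by pooling; the synopsis (Statistical Methods) says: "Patients receiving placebo in Part 2b will be pooled with the placebo cohort from Part 2a". Section 6 repeats this.

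For collection, Section 5.3.1 states that after the first dose "all adverse events, regardless of relationship to study drug, will be reported until the last follow-up visit". Section 3.1.1 sets the end of follow-up for Part 2a as "Safety Follow-up: up to at least Day 113", with the same day for the Part 2b 3-dose and 5-dose regimens. For the 4-dose weekly regimen it is "Safety Follow-up: Up to at least Day 106". In Part 2c, Cohort 9 is dosed for up to 24 weeks and Cohort 10 for up to 48 (4.4.2.1). Follow-up adds 24 weeks, and the schedules in Appendices 11 and 13 end at Week 48 and Week 72.

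For reporting, Section 6 says summaries are descriptive and "will be reported separately for each part of the study within the clinical study report". Under 6.5, safety data "will be listed and summarized descriptively", and 6.5.1 adds: "AEs will be described by individual listings and frequency tables broken down by body system". Section 3.3.1 and the synopsis also list incidence of laboratory abnormalities as a safety outcome. Section 6 and the synopsis give no common window and no patient-time denominator for these incidences.

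**The concern.** A frequency table counts patients with at least one event during the time they were observed. If one group is observed three to almost five times as long as the other, its percentages will tend to be higher even when the underlying rates are identical. A reader who sets the Part 2c tables beside the placebo tables, as 3.2.3 invites, cannot tell how much of a difference is due to treatment and how much to the calendar.

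The same holds for cumulative incidence of laboratory abnormalities, which also rises with the number of samples taken. Laboratory and ECG summaries by time point (6.5.2, 6.5.4) are not affected.

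Pooled Part 2a/2b placebo is the only in-study comparator for Part 2c. Accumulated safety data also feed the decision to expand cohorts or open optional ones (3.1.2). What is at stake is misreading in either direction: an apparent excess produced by observation time, or a real excess dismissed as the effect of longer follow-up.

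**Working it through.** **Check on the plan's own durations (synopsis, Length of Study).** Weeks after first dose = (last day − 1)/7.
- Day 113: 112/7 = 16 weeks. With 8 weeks of screening, 24 weeks, as stated for Part 2.
- Day 106: 105/7 = 15 weeks. With screening, 23 weeks, as stated for Cohort 8.
- Part 2c, shortest case: 4 + 24 + 24 = 52 weeks, as stated.

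**AE collection periods from first dose.**
- Parts 2a/2b: 15 or 16 weeks.
- Cohort 9: 24 + 24 = 48 weeks. Ratio 48/16 = 3.0 to 48/15 = 3.2.
- Cohort 10: 48 + 24 = 72 weeks. Ratio 72/16 = 4.5 to 72/15 = 4.8.

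The synopsis instead counts 112 or 105 days from the last dose. Read literally, that is (28 + 112)/7 = 20 weeks or (21 + 105)/7 = 18 weeks. The ratios are then 2.4 to 2.7 and 3.6 to 4.0, so the imbalance remains.

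**Illustration with no drug effect.** The documents give no placebo-only AE rate, so the incidence p at 16 weeks is an assumption. Incidence over the longer period is 1 − (1 − p)^k.
- Constant hazard: k = 48/16 = 3 and 72/16 = 4.5.
- Hazard falling to a quarter after week 16: k = 1 + 0.25 × 2 = 1.5 and 1 + 0.25 × 3.5 = 1.875.

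| p at 16 weeks | Constant hazard, 48 / 72 weeks | Quarter hazard, 48 / 72 weeks |
|---|---|---|
| 10% (assumed, nearer a single body system) | 27% / 38% | 15% / 18% |
| 30% (assumed, nearer any AE) | 66% / 80% | 41% / 49% |
| 59% (32/54) | 93% / 98% | 74% / 81% |

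For example, 1 − 0.9^3 = 0.271 and 1 − 0.7^1.875 = 0.488. The 59% is the only documented incidence in these patients (1.2.2: 32 of 54). It mixes active and placebo at a data cut-off, so it is a reference point and not a placebo rate.

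**Why a single patient-time rate would not settle it.** Under the quarter hazard, the full-period rate relative to the 16-week rate is 1.5/3 = 0.50 in Cohort 9 and 1.875/4.5 = 0.42 in Cohort 10, again with no drug effect. That bias runs the other way.

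**Group sizes.** About 8 per initial Part 2c cohort. Planned placebo is 6 (Part 2a) + 2 × 3 cohorts (Part 2b) = about 12.

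**The case against.** The strongest reply is that the comparison is declared qualitative, the summaries descriptive and the study hypothesis-generating (6.11). No threshold or decision rule is attached to the placebo contrast, and 3.2.3 names a second comparator, historical standard-of-care profiles. This stands and limits the point to interpretation.

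A reader might go further and infer that the plan carries a high probability of a false safety signal. With 8 against 12 patients and p = 30%, the exact binomial chance of a crude gap of at least 20 points is 19% with equal windows, and 79% (Cohort 9) or 94% (Cohort 10) with the planned periods under a constant hazard. The documents do not support reading these as error rates: no 20-point criterion is planned and 30% is an assumption. At 10%, closer to the body-system tables that 6.5.1 describes, the figures are 43% and 67% (constant) or 16% and 22% (quarter hazard), against 8% with equal windows.

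It can also be said that individual listings let a reader pick out early events, that 6.5 allows further tables as appropriate, and that reporting by part may mean Part 1 against Part 2. All fair: nothing forbids a common-window table. But none is specified, so any selection of events would be made after the data are seen.

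Finally, equal windows remove only one difference. Part 2c is open-label while Parts 2a/2b are blinded; eligibility differs, including the ALT limits (4.2.2.2, 4.2.2.3); weekly clinic dosing gives more contacts; and severity is graded on different scales (5.3.3). This is true and belongs in footnotes, but observation length is the difference that a table can remove at little cost.

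**Conclusion.** The point holds as a modest reporting gap. AE incidence and laboratory-abnormality incidence will accumulate over periods that differ by a factor of 3.0 to 4.8 (2.4 to 4.0 on the literal synopsis reading), and the direction is known: upward in Part 2c. The size depends on the assumed rate and on how the hazard changes with time. With no drug effect it ranges from a rise of 5 points (10% to 15%, Cohort 9, quarter hazard) to one of 50 points (30% to 80%, Cohort 10, constant hazard).

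Two wider readings are not supported. One is that laboratory safety is untouched: that is true only of the by-time-point summaries. The other is that a common window would make Part 2c a controlled comparison: it would still be non-randomised, open-label and imprecise at about 8 against 12 patients.

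**What to change.** In Section 6.5, add one table of AE incidence and one of incidence of laboratory abnormalities, each showing every Part 2c cohort and pooled Part 2a/2b placebo over a single window from first dose to Day 106, the shortest nominal follow-up. Place them beside the full-period Part 2c tables so that late events are kept.

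State how patients observed for less time are counted. The Day 106 visit has a ±7-day window (Appendix 7), so a compliant last visit can fall on Day 106 − 7 = 99, and some patients will withdraw early. Either show the number still under observation at Day 106 or cut at Day 99. If events per patient-time are also shown, split them at the cut.

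Footnote what remains different: severity scale, PEG-IFN in Cohort 10 (which prevents attribution to RO7062931 alone), Part 2c dosing continuing within the window after Part 2a/2b dosing has ended by Day 29, open-label against blinded conduct, eligibility, and contact frequency.

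The cost is one extra set of tables and no new data. The window omits late Part 2c events, which stay in the full-period tables.

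Separately, and without bearing on the argument above, the follow-up wording needs reconciling. Sections 3.1.1 and 3.1.1.2 agree (Day 29 + 84 = 113; Day 22 + 84 = 106), but the synopsis gives Day 29 + 112 = 141 and Day 22 + 105 = 127. Part 2c follow-up is a maximum of 24 weeks in 3.1.1 and a minimum of 24 weeks in 3.1.1.3.
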